3.0 Protocol Objectives

The overall objective of this study is to use standard clinical measures to explore the safety and effects of open-label manualized MDMA-assisted psychotherapy with a flexible dose of MDMA in participants with severe PTSD, and to serve as an opportunity for supervision of therapy teams selected to conduct Phase 3 MDMA-assisted psychotherapy research.

3.1 Primary Objective

1. The primary objective of this study is to evaluate the effect of MDMA-assisted psychotherapy on PTSD, as measured by the estimand of change in CAPS-5 Total Severity Score from Baseline (Visit 3) to 18 weeks post Baseline (Visit 19).

3.2 Secondary Objective

1. The secondary objective is to evaluate the effect of MDMA-assisted psychotherapy for PTSD in clinician-rated functional impairment, as measured by the mean change in Sheehan Disability Scale (SDS) item scores from Visit 3 (Baseline) to Visit 19 (18 weeks post Baseline).

3.3 Safety Objectives

The overall safety objective is to assess severity, incidence and frequency of AEs, AEs of Special Interest (AESIs), and Serious Adverse Events (SAEs), concomitant medication use, suicidal ideation and behavior, and vital signs to support the package insert for MDMA-assisted psychotherapy. The following safety objectives will evaluate the safety of MDMA-assisted psychotherapy.

- 1. Assess incidence of AEs during Experimental Sessions that may be indicative of a medical complication of the Investigational Product (IP), such as clinical signs and symptoms of chest pain, shortness of breath, or neurological symptoms or any other signs or symptoms that prompt additional vital sign measurements
- 2. Assess incidence of AEs by severity
- 3. Assess incidence of Treatment Emergent AEs (TEAEs) by severity
- 4. Assess incidence of TEAEs by severity taken during an Experimental Session and 2 days after IP administration
- 5. Assess incidence of AESIs, defined as AEs specified in the protocol related to cardiac function and abuse liability
- 6. Assess incidence of AEs by severity categorized as leading to discontinuation of IP, resulting in death or hospitalization, and continuing at Study Termination
- 7. Assess incidence of SAEs
- 8. Assess incidence of psychiatric concomitant medications taken during an Experimental Session and 2 days after IP administration
- 9. Assess incidence of any psychiatric concomitant medications taken during the Treatment Period

- MP16 Protocol Amendment 1 Version 1: 03 January 2018
- 10. Assess incidence of serious suicidal ideation and positive suicidal behavior assessed with the Columbia Suicide Severity Rating Scale (C-SSRS)
- 11. Assess mean changes in blood pressure, heart rate, and body temperature from pre-IP administration to end of each Experimental Session

3.4 Exploratory Objectives

These objectives may be explored to characterize participants receiving MDMA-assisted psychotherapy to support the primary objective:

- 1. Explore the effect of presence of secondary traumatic stressors (LEC-5) on the CAPS-5 Total Severity analyses
- 2. Explore changes within-participants in PTSD symptom clusters of re-experiencing, avoidance, negative alterations in cognition and mood, and hyperarousal, as measured by changes in CAPS-5 subscale scores from Visit 3 (Baseline) to Visit 19 (18 weeks post Baseline)
- 3. Explore the effect of adverse childhood experiences (ACE) on the CAPS-5 Total Severity analyses
- 4. Explore changes in:
 - Dissociative symptoms associated with PTSD (DSP-I)
 - Depression (BDI-II)
 - Chronic pain (CPGS)
 - Quality of life (EQ-5D-5L)
 - Functioning in relation to self and others (IASC)
 - Psychosocial functioning (IPF)
 - Self-compassion (SCS)
 - Alexithymia (TAS-20)
 - Addictive behaviors including: alcohol use (AUDIT), drug use (DUDIT), and nicotine use (SRNU)
 - Eating habits (EAT-26)
 - Workplace productivity (HPQSF)
 - Healthcare utilization (UFEC)

4.0 Eligibility Criteria

4.1 Inclusion Criteria

At the completion of Screening, participants must meet all eligibility criteria (except Inclusion Criterion #13) and agree to all lifestyle modifications to be enrolled. Each participant will then enter the Preparatory Period which includes medication tapering, if needed, and non-drug Preparatory Sessions. The Preparatory Period ends with Enrollment Confirmation. A participant's enrollment will be confirmed if they have completed medication tapering, have a confirmed PTSD diagnosis per the CAPS-5 assessment and a Total Severity Score of 35 or greater, continue to agree to all lifestyle modifications, and continue to meet all eligibility criteria (those criteria marked with an * below will only be assessed at Screening, since they will not change).

Potential participants are eligible to enroll in the protocol if they:

- 1. *Are at least 18 years old
- 2. *Are fluent in speaking and reading the predominantly used or recognized language of the study site
- 3. *Are able to swallow pills
- 4. Agree to have study visits recorded, including Experimental Sessions, Independent Rater assessments, and non-drug psychotherapy sessions
- 5. Must provide a contact (relative, spouse, close friend or other support person) who is willing and able to be reached by the investigators in the event of a participant becoming suicidal or unreachable
- 6. Must agree to inform the investigators within 48 hours of any medical conditions and procedures
- 7. If of childbearing potential, must have a negative pregnancy test at study entry and prior to each Experimental Session, and must agree to use adequate birth control through 10 days after the last Experimental Session. Adequate birth control methods include intrauterine device (IUD), injected or implanted hormonal methods, abstinence, oral hormones plus a barrier contraception, vasectomized sole partner or double barrier contraception. Two forms of contraception are required with any barrier method or oral hormones (i.e. condom plus diaphragm, condom or diaphragm plus spermicide, oral hormonal contraceptives plus spermicide or condom). Not of childbearing potential is defined as permanent sterilization, postmenopausal, or assigned male at birth.
- 8. Agree to the following lifestyle modifications (described in more detail in Section 4.3 Lifestyle Modifications): comply with requirements for fasting and refraining from certain medications prior to Experimental Sessions, not participate in any other interventional clinical trials during the duration of the study, remain overnight at the study site after each Experimental Session and be driven home after, and commit to medication dosing, therapy, and study procedures

Medical History

- 9. *At Screening, meet DSM-5 criteria for current PTSD with a symptom duration of 6 months or longer
- 10. *At Screening, have at least severe PTSD symptoms in the last month based on PCL-5 total score of 50 or greater
- 11. *At Screening, may have well-controlled hypertension that has been successfully treated with anti-hypertensive medicines, if they pass additional screening to rule out underlying cardiovascular disease
- 12. *At Screening, may have asymptomatic Hepatitis C virus (HCV) that has previously undergone evaluation and treatment as needed
- 13. At Baseline, have at least severe PTSD per CAPS-5 and symptoms in the last month constituting a CAPS-5 Total Severity Score of 35 or greater.

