 provided records. If no records were provided or those provided are not sufficient,
 request additional records. Collect data on previous hospitalizations and healthcare
 utilization.
- Support the participant during completion of the LEC-5 with PCL-5 to confirm PTSD diagnosis and severity. Support is needed to ensure proper identification of the index trauma on the PCL-5. Symptom severity is assessed in relation to the index trauma.
- Administer the Lifetime C-SSRS to assess history of suicidal behavior and ideation
- Review past and current medications and adherence to prescriptions
- Assess childbearing potential and discuss requirement for commitment to adequate birth control for the duration of the study. Perform urine pregnancy test for participants who are of childbearing potential.
- Perform a urine drug test

- Direct participant to complete self-reported Screening measures:
 - o SCID-5-SPO
 - o AUDIT
 - o DUDIT
- Review results of all measures and discussions against eligibility criteria to assess initial eligibility. If deemed initially eligible, potential participant will be provided with instructions (and appointments, if applicable) for a physical exam, laboratory assessments, an electrocardiogram (ECG), and 1-minute rhythm strip. Some or all of these assessments may be at outside facilities.

MP16 Protocol

Amendment 1 Version 1: 03 January 2018

Medical Assessments

The physical exam must be performed by a qualified physician and lab assessments must be completed at a designated lab. Medical assessments will include:

- Blood pressure, pulse, and body temperature measurement
- Height and weight, which will be used to calculate Body Mass Index (BMI)
- Examination of head, eyes, ears, nose, throat, skin, heart, lungs, abdomen, and extremities
- Brief neurological exam (cranial nerves 2-12, sensory, motor, reflexes, and cerebellar function)
- ECG and 1-minute rhythm strip
- Clinical laboratory assessments, per Section 13.0 Clinical Laboratory Assessments. The
 clinical laboratory values will not be captured in the eCRF, but will be used to establish
 eligibility and will be kept with the participant's source record. Clinically significant
 abnormal values will be captured as medical history.
- If there is evidence of liver disease by history, physical examination or laboratory testing, HCV serology will be performed.

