10.2.3.4 Reproductive and Developmental Risks and Mitigation

Risks posed by MDMA to pregnant people are not known. One of two studies of Ecstasy users suggests that use of Ecstasy and other drugs during pregnancy may be associated with some abnormalities at birth while the other failed to find this association [115, 116].

Pregnant and lactating people will be excluded from participation in the study. Participants who are able to become pregnant must have a negative pregnancy screen before undergoing each Experimental Session and must agree to use adequate birth control for the duration of the study during the Treatment Period. Procedures described in Section 11.3 Pregnancy have been put in place to mitigate risk of reproductive or developmental exposure to the IP.

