11.3.2 Contraception Guidelines

Adequate birth control methods are required for participants of childbearing potential and include:

- Intrauterine device (IUD)
- Intrauterine hormone-releasing system (IUS)
- Non-oral hormonal methods, including injected, intravaginal, implanted, transdermal
- Oral hormones plus a barrier contraception (condom, diaphragm, or spermicide)
- Double barrier method (at least two of the following: condom, diaphragm, and spermicide)
- Vasectomized sole partner
- Abstinence from penile-vaginal intercourse
 - The reliability of abstinence should be evaluated carefully with the participant in relation to their general lifestyle. An additional acceptable birth control method should be discussed with the participant in case they decide to engage in penilevaginal intercourse during the course of the study.

For questions about acceptable birth control methods, contact the Medical Monitor.

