11.3.3 Follow-up Requirements

Details of all pregnancies in study participants will be collected after Enrollment (Visit 0) and collected through 10 days after the last Experimental Session. Pregnancies should be reported to the sponsor via telephone or email within 24 hours of site staff awareness.

In the event of a pregnancy, the participant will discontinue Experimental Sessions but may continue with non-drug Integrative Sessions, the next CAPS-5 assessment, and Study Termination procedures. At a minimum, prior to withdrawal from the study, efforts should be made to assess the final CAPS-5 immediately and complete Study Termination procedures.

The investigator will collect follow-up information on the participant and neonate and forward to the sponsor until the outcome of the pregnancy, which will be reported on an optional Pregnancy eCRF. Any termination, elective or spontaneous, will be reported. Abnormal pregnancy outcomes, such as spontaneous abortion, fetal death, stillbirth, congenital abnormalities, or ectopic pregnancy, will be reported as SAEs.

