Participants may return to taking psychiatric medications and discontinue birth control after the final Study Termination visit if necessary.

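### The protocol gives conflicting end points for required contraception and two differing method lists, and it closes pregnancy collection at day 10, so a pregnancy conceived around the last dose can go uncollected

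*Protocol*

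**What the plan says.** **End of required contraception.** Four places in the protocol address it.

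- Section 4.1, criterion 7: the participant "must agree to use adequate birth control through 10 days after the last Experimental Session".
- Section 8.1.1, Screening: site staff are to "discuss requirement for commitment to adequate birth control for the duration of the study".
- Section 10.2.3.4: participants who can become pregnant "must agree to use adequate birth control for the duration of the study during the Treatment Period".
- Section 12.1: "Participants may return to taking psychiatric medications and discontinue birth control after the final Study Termination visit if necessary".

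**Accepted methods.** Criterion 7 names an intrauterine device, "injected or implanted hormonal methods, abstinence, oral hormones plus a barrier contraception", a vasectomised sole partner and double barrier. Its examples of paired methods give "oral hormonal contraceptives plus spermicide or condom". Section 11.3.2 adds an intrauterine hormone-releasing system, accepts "Non-oral hormonal methods, including injected, intravaginal, implanted, transdermal", and allows a diaphragm as the barrier used with oral hormones.

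**Pregnancy collection.** Section 11.3.3 states: "Details of all pregnancies in study participants will be collected after Enrollment (Visit 0) and collected through 10 days after the last Experimental Session". It then asks for a report within 24 hours of the site learning of a pregnancy, for follow-up of participant and neonate to outcome, and for abnormal outcomes to be reported as SAEs. Sections 11.1 and 11.1.2 collect AEs and SAEs through Study Termination. Table 5 schedules the last pregnancy test at Visit 15, and Section 8.3.1 places it before dosing.

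**The concern.** A site cannot tell from the protocol when a participant may stop contraception. The eligibility commitment, the screening discussion, the risk section and the medication section give different answers. The two method lists also leave room for sites to treat the same method differently.

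The pregnancy window is the more consequential part for the data. Ten days after Session 3 may suit a rule about exposure, but the same limit is applied to collection, and a pregnancy has to be recognised before it can be collected. No test is scheduled after the last dose. Section 10.2.3.4 says the risk of MDMA in pregnancy is not known, and Section 5.1 sends all data to the sponsor's safety database. In a study of at most 60 participants, any exposed pregnancy is scarce information. Follow-up to outcome appears to open only for pregnancies collected in the first place.

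**Working it through.** The plan states no figure of its own here, so the check is date arithmetic on the visit windows, with Session 3 (Visit 15) as day 0.

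**Step 1. When Visit 20 falls.** Inputs: Visit 19 is 8 (±2) weeks after Session 3 (Section 8.4.2); Visit 20 is 2 (−1/+7) days after Visit 19 (Section 8.4.3).

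- Earliest: 6 × 7 + 1 = day 43
- Nominal: 8 × 7 + 2 = day 58
- Latest: 10 × 7 + 9 = day 79

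**Step 2. Gap from day 10 to Visit 20.** 43 − 10 = 33; 58 − 10 = 48; 79 − 10 = 69 days. This is the difference between the criterion 7 and Section 12.1 end points. It is also the period in which AEs and SAEs are collected but pregnancies, on the plain reading, are not.

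**Step 3. The Treatment Period reading of Section 10.2.3.4.** That period ends at Visit 18, which Section 8.3.3 places 3 to 5 weeks after Session 3 (days 21 to 35) and Table 1 places within 4 weeks (by day 28). On the Section 8.3.3 timing, this end point is 11 to 25 days later than criterion 7.

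**Step 4. Can a pregnancy near the last dose be recognised by day 10?** Assumption: recognition comes L days after conception, with L from 10 to 28. A pregnancy conceived on day c is inside the window only if c + L ≤ 10.

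- For c = 0, recognition is on day L. It is inside the window only at L = 10 and outside for every longer lag.
- For conceptions spread evenly over days −7 to +7 (14 days), the share recognised after day 10 is:

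| L (days) | Recognised by day 10 | Share after day 10 |
|---|---|---|
| 10 | 7 of 14 | 50% |
| 14 | 3 of 14 | 79% |
| 21 | 0 of 14 | 100% |
| 28 | 0 of 14 | 100% |

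**Step 5. A stricter definition of exposed.** Section 2.2.2 gives a half-life of 7 to 9 hours, so five half-lives are 35 to 45 hours, at most 45/24 = 1.875 days. Count only conceptions too recent to be recognised at the Session 3 test (after day −L) and no later than day 1.875. That span is L + 1.875 days, of which the first 10 days' worth are recognised by day 10. The share recognised later is 1 − 10/(L + 1.875): 16% at L = 10, 37% at L = 14, 56% at L = 21 and 67% at L = 28.

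**Step 6. Would Visit 20 be late enough?** Taking the latest conception as day 10 and the longest lag as 28 days, recognition is by day 10 + 28 = 38, before the earliest Visit 20 on day 43.

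**The case against.** Much can be said on the other side.

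- **Method lists.** Both lists are introduced as inclusive, so neither is stated to be exhaustive. Exclusion criterion 23 asks only for an effective method, and Section 11.3.2 refers questions to the Medical Monitor. A reader might infer that a patch or ring user fails criterion 7. The documents do not support that: the method is simply not named there. The general wording of criterion 7 on oral hormones would also admit a diaphragm; only its examples omit it.
- **Other reporting routes.** The 24-hour reporting sentence has no end date. Abnormal outcomes are SAEs, collected to Study Termination. Criterion 6 commits participants to report medical conditions within 48 hours, and sites ask about health changes at Visits 17, 18 and 20. Section 11.3.3 can also be read as covering pregnancies that begin by day 10, whenever noticed. A reader might infer that late-recognised pregnancies are certain to be lost, but these routes rule that out. What remains is chiefly a pregnancy without an abnormal outcome, recognised after day 10 and handled on the plain reading. The availability of two readings is itself a reason to clarify the text.
- **Exposure.** With a half-life of 7 to 9 hours, conceptions from about day 2 follow near-complete elimination. This narrows the group of interest, and Step 5 allows for it. It does not close the gap, because the half-life governs when exposure ends and not when an exposed pregnancy becomes known.
- **Protection.** Every stated contraception end point reaches at least day 10, so the conflict does not shorten cover below criterion 7.
- **Weight.** Pregnancy is not among the safety objectives in Section 3.3, and the expected count is small.

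**Conclusion.** The point stands as an internal contradiction with a limited consequence for safety data. The day-10 and Study Termination end points differ by 33 to 69 days (nominally 48), and the Treatment Period wording adds a third possible date. The method lists differ on intrauterine hormonal, intravaginal and transdermal methods and on the diaphragm with oral hormones, so sites may decide inconsistently; the documents do not show that they would.

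On the plain reading of Section 11.3.3, a pregnancy conceived around the last dose can go uncollected, together with its follow-up to outcome. The shares in Steps 4 and 5 rest on an assumed recognition lag of 10 to 28 days and evenly spread conceptions, neither of which is in the documents. They show how the window behaves and do not predict a number of missed pregnancies.

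A reader might also infer that one end point or one method list is the correct one. Nothing here decides that. The conflict is textual, and its resolution is a clinical decision for the sponsor. No efficacy result is affected.

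**What to change.** State in Section 11.3.3 that pregnancies are collected through Visit 20, using the health-change questions already asked at Visits 17, 18 and 20, and record the estimated conception date relative to each dose. Under the assumed lags, this would bring in every conception up to day 10 (Step 6).

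Reconcile Sections 4.1, 8.1.1, 10.2.3.4 and 12.1 to one contraception end point, and Sections 4.1 and 11.3.2 to one method list. The sponsor's medical team should decide the content of both.

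The cost is a protocol amendment with its usual ethics and regulatory review, matching consent wording if needed (the consent form was not available for this review), and a slightly longer pregnancy reporting period for sites. No visit or test is added.

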4.2 Exclusion Criteria

Potential participants are ineligible to enroll in the protocol if they:

- 1. *Are not able to give adequate informed consent
- 2. Are currently engaged in compensation litigation whereby financial gain would be achieved from prolonged symptoms of PTSD or any other psychiatric disorders
- 3. Are likely, in the investigator's opinion and via observation during the Preparatory Period, to be re-exposed to their index trauma or other significant trauma, lack social support, or lack a stable living situation

- 4. Have used Ecstasy (material represented as containing MDMA) more than 10 times within the last 10 years or at least once within 6 months of the first Experimental Session; or have previously participated in a MAPS-sponsored MDMA clinical trial
- 5. Have any current problem which, in the opinion of the investigator or Medical Monitor, might interfere with participation

Psychiatric History

- 6. *Have received Electroconvulsive Therapy (ECT) within 12 weeks of enrollment
- 7. *Have a history of, or a current primary psychotic disorder, bipolar affective disorder type 1 assessed via MINI or dissociative identity disorder assessed via DDIS
- 8. *Have a current eating disorder with active purging assessed via MINI
- 9. *Have current major depressive disorder with psychotic features assessed via MINI
- 10. *Meet DSM-5 criteria for active substance use disorder for any substance other than caffeine or nicotine in the past 60 days assessed via MINI, AUDIT, DUDIT, drug test, and blood %carbohydrate-deficient transferrin (%CDT)
- 11. Have current Personality Disorders Cluster A (paranoid, schizoid, schizotypal), Cluster B (antisocial, borderline, histrionic, narcissistic), or Cluster C (avoidant, dependent, obsessive-compulsive) assessed via SCID-5-PD. Diagnoses will be confirmed via clinical interview
- 12. Any participant presenting current serious suicide risk, as determined through psychiatric interview, responses to C-SSRS, and clinical judgment of the investigator will be excluded; however, history of suicide attempts is not an exclusion. Any participant who is likely to require hospitalization related to suicidal ideation and behavior, in the judgment of the investigator, will not be enrolled
- 13. Would present a serious risk to others as established through clinical interview and contact with treating psychiatrist
- 14. Require ongoing concomitant therapy with a psychiatric medication with exceptions described in Section 12.0: Concomitant Medications

Medical History

- 15. *Have evidence or history of significant (controlled or uncontrolled) hematological, endocrine, cerebrovascular, cardiovascular, coronary, pulmonary, renal, gastrointestinal, immunocompromising, or neurological disease, including seizure disorder, or any other medical disorder judged by the investigator to significantly increase the risk of MDMA administration (participants with hypothyroidism who are on adequate and stable thyroid replacement will not be excluded). Note: if participants present with a history of glaucoma, enrollment would be allowed only with the approval of their ophthalmologist
- 16. *Have uncontrolled hypertension using the standard criteria of the American Heart Association (values of 140/90 milligrams of Mercury [mmHg] or higher assessed on three separate occasions)
- 17. *Have a marked baseline prolongation of QT/QTc interval (e.g., repeated demonstration of a QTc interval >450 milliseconds [ms] corrected by Bazett's formula)
- 18. *Have a history of additional risk factors for Torsade de pointes (e.g., heart failure, hypokalemia, family history of Long QT Syndrome)
- 19. *Require use of concomitant medications that prolong the QT/QTc interval during Experimental Sessions. Refer to Section 12.0 Concomitant Medications.
- 20. *Have symptomatic liver disease
- 21. *Have history of hyponatremia or hyperthermia
- 22. *Weigh less than 48 kilograms (kg)
- 23. Are pregnant or nursing, or are of childbearing potential and are not practicing an effective means of birth control.

